4.8 MISSING DATA

All data collected under this study protocol will be included in the assessment of subject safety. Missing or incomplete AE data will assume greatest relationship to study drug and/or severity.

For the exploratory effectiveness endpoints (WOMAC A, WOMAC C, and PGA), missing values will be imputed when the ITT analysis population is used. The Worst Observation Carried Forward (WOFCF) will be selected as the primary method of imputing missing data. Alternate imputation methods that may be employed will include multiple imputations (SAS PROC MI and SAS PROC MIANALYZE) and Last Observation Carried Forward (LOCF).

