All efficacy variables will be assessed at Visit 9 (Day 0), Visit 11 (Day 84 ± 14), Visit 13 (Day 168 ± 14), Visit 15 (Day 252 ± 14), and Visit 17 (Day 280 ± 14). Except where noted to be otherwise, all statistical tests will be two-sided and will be at the 5% level of significance.

Unless otherwise specified, continuous variables will be summarized with the number of non-missing observations, mean, standard deviation, median, minimum, and maximum displayed. Categorical data will be summarized as counts and percentages. All efficacy assessments will be summarized as the measured value and as the change from baseline by treatment at each time point. Summary statistics will include number of observations, mean, standard deviation, median, minimum and maximum. Change from baseline will also include a 95% confidence interval.

Except where otherwise specified, missing data will not be estimated or carried forward in any of the descriptive analyses. No multiple comparison adjustment will be made for the secondary efficacy analyses. Data transformation or use of rank-based tests may be used if endpoints depart substantially from a normal distribution.

Baseline (Day 0 of AP-003-C main study) is defined as the last pre-treatment assessment. Because the secondary analyses are considered supportive to the primary analysis (i.e., not required to demonstrate efficacy of the test article), there is no requirement under ICH to adjust for multiplicity

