10.5 MISSING AND SPURIOUS DATA

All data collected under this study protocol will be included in the assessment of subject safety. Missing or incomplete AE data will assume greatest relationship to study drug and/or severity.

For the exploratory effectiveness endpoint analyses (WOMAC and PGA), missing scores will be imputed in when the worst observation carried forward to aid in the assessment of the robustness of the results.

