4. HYPOTHESES AND METHODS

4.1 Primary Analysis Methodologies

Since this is an observational study on the repeat administration of Ampion 4 mL injection, no formal hypotheses will be tested in this study. There will be no comparisons made to threshold values or to “historical” control values. There is no comparator in this study.

All analyses will be descriptive in nature and will be performed at each efficacy assessment (Visit 9 (Enrollment), Visit 11 (Week 12), Visit 13 (Week 24), Visit 15 (Week 36) and Visit 17 (Week 40)). For dichotomous outcomes, the percentage of patients with that outcome will be estimated and exact 95% binomial confidence intervals will be calculated. These dichotomous outcomes are:

- The incidence of treatment emergent adverse events
- Responder status based on the OMERACT-OARSI responder criteria
- Evaluate OMERACT-OARSI ‘controlled’ responder defined as a 20% improvement in Pain and Function and 0.5 point absolute change in the 5-point Likert Scale
- Evaluate 20% improvement in PGA and 0.5 point absolute change in the 5-point Likert Scale

The outcomes with more continuous responses will be analyzed via descriptive statistics (n, mean, standard deviation, median, minimum, and maximum). Also, 95% confidence intervals from the mean response will be calculated. These outcomes are:

- Mean change and percent change in WOMAC A pain subscore
- Mean change and percent change in WOMAC B stiffness subscore
- Mean change and percent change in WOMAC C physical function subscore
- Mean change and percent change in PGA
- Mean Change and percent change in WOMAC A pain subscore questions 1 and 2 (pain with movement)
- Mean Change and percent change in WOMAC A pain subscore questions 3–5 (resting pain)
- Change in contralateral knee pain (WOMAC A)
- Change in contralateral knee stiffness (WOMAC B)
- Change in contralateral knee function (WOMAC C)

Differences in pain scores between successive visits will be estimated via descriptive statistics and confidence intervals.

The time to total knee replacement will be summarized using Kaplan-Meier methodologies. The use of rescue analgesia will be summarized as the dichotomous outcome on the number of patients using rescue medication and as continuous variables on the number of medications use.

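### SAP 4.8 turns worst observation carried forward from the protocol's robustness check into the primary ITT method without declaring it, shifting WOMAC A, WOMAC C and PGA estimates toward less improvement

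*SAP*

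**What the plan says.** Protocol 10.3.11.5 gives the default: "Except where otherwise specified, missing data will not be estimated or carried forward in any of the descriptive analyses". Protocol 10.5 is an exception for WOMAC and PGA, with a stated purpose: "missing scores will be imputed in when the worst observation carried forward to aid in the assessment of the robustness of the results".

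SAP 4.8 assigns the method a different role. Its scope is: "For the exploratory effectiveness endpoints (WOMAC A, WOMAC C, and PGA), missing values will be imputed when the ITT analysis population is used". It then says: "The Worst Observation Carried Forward (WOFCF) will be selected as the primary method of imputing missing data". The other methods are optional: "Alternate imputation methods that may be employed will include multiple imputations", with last observation carried forward also named.

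SAP 4.1 says of the planned analyses: "All analyses will be descriptive in nature". For the continuous outcomes it adds: "Also, 95% confidence intervals from the mean response will be calculated". The protocol likewise says: "Change from baseline will also include a 95% confidence interval".

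SAP Section 6, which is headed as the place for changes from protocol-specified analyses, has only general text and does not mention missing data.

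**The concern.** The two documents prescribe different main efficacy results. Under the protocol, the descriptive tables rest on observed scores and WOCF shows how far they could move. Under the SAP, the WOCF figures are the ITT result, and nothing tells the reader of the study report that the role has changed.

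This is a single-arm study with no formal efficacy test, so its efficacy output is the estimate and its interval. A shift built into the estimate is not offset by a comparator treated in the same way.

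The rule is also incomplete:

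- It does not say whether a pre-treatment score can be the worst observation. Entry required a pain score of at least 1.5 in the main study (Protocol 4.2), and SAP 4.1 also measures change from the main-study baseline. If such scores count, WOCF is close to carrying baseline forward.
- WOMAC B and the two pain sub-scores (questions 1–2 and 3–5) are not named, although Protocol 10.5 refers to WOMAC as a whole.
- SAP Section 7 requires every efficacy table for both ITT and per-protocol populations, but imputation is tied to ITT. An ITT versus per-protocol difference then mixes population with missing-data method.

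**Working it through.** **The plan's own figure.** Protocol 10.3.7 takes 15% dropout from 161 subjects: 161 × 0.85 = 136.85, given as 136. This reproduces. It implies 25 missing at the final visit, so f = 25/161 = 0.155. Neither document states an SD, interval width or power for this study.

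**Inputs.** Mean WOMAC A change −0.82 and SD s = 0.817 (Protocol Table 1.5.2, Ampion, KL 4, studies combined), assumed to carry over from 12-week single-injection data. Within-subject correlation, baseline distribution and dropout pattern are assumptions.

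**Shift.** If imputed changes are on average d points worse than observed ones, the mean moves by f × d. Carrying baseline forward gives d = 0.82: 0.155 × 0.82 = 0.127, so −0.82 becomes −0.69. The shift is larger when some scores were worse than baseline.

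**Width.** Observed cases: 1.96 × 0.817/√136 = 0.137. WOCF: 1.96 × √(V/161), with V = (1 − f)s² + f·s_m² + f(1 − f)d², where s_m is the SD of the imputed changes. With s_m = 0.817:

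- d = 0: 0.126 (8% narrower)
- d = 0.82: 0.134 (2% narrower)
- d = 1.0: 0.138 (0.5% wider)
- d = 1.5: 0.152 (10% wider)

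Break-even is d = 0.97 for s_m = 0.817 and d = 1.31 for s_m = 0.

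**Simulation.** 161 subjects, four post-enrolment visits, about 15% dropout, 1,500 runs per setting, correlations 0.3, 0.5 and 0.7; ranges are over the correlations. The target is the no-dropout mean, −0.82.

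| Dropout | Analysis | Mean | Coverage | Width relative to observed cases |
|---|---|---|---|---|
| Random | Observed cases | −0.82 | 94–95% | 1 |
| Random | WOCF, pre-treatment counted | −0.68 | 41–43% | 0.936–0.938 |
| Random | WOCF, not counted | −0.77 to −0.79 | 88–93% | 0.923–0.925 |
| Follows poor response | Observed cases | −0.87 to −0.90 | 80–89% | 1 |
| Follows poor response | WOCF, pre-treatment counted | −0.71 to −0.73 | 62–72% | 0.971–0.985 |
| Follows poor response | WOCF, not counted | −0.78 to −0.79 | 89–93% | 0.954–0.965 |

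A second simulation (random dropout, correlation 0.6) required baseline pain of at least 1.5 (mean 2.3, SD 0.5 assumed) and floored scores at 0, which makes the true mean −0.80. WOCF gave −0.67 (coverage 42–44%) with pre-treatment scores counted, and −0.76 to −0.78 (coverage 89–93%, depending on how dropout timing was coded) without. Shifts under random dropout are therefore about 0.13–0.14 and 0.02–0.05.

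**Where the coverage goes.** Take correlation 0.5 and random dropout.

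- Pre-treatment counted: shift 0.82 − 0.679 = 0.141, SE 0.1282/1.96 = 0.0654, ratio 2.16. Coverage from the shift alone is Φ(1.96 − 2.16) ≈ 0.42; simulated 0.41.
- Not counted: shift 0.040, SE 0.1261/1.96 = 0.0643, ratio 0.62. Coverage is Φ(1.34) − Φ(−2.58) ≈ 0.905; simulated 0.90.

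The shift accounts for essentially all of the loss. Centred on WOCF's own expected value, the intervals cover 94–95%.

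**Responder rates.** If the relevant baseline counts as an observation, no imputed score can show improvement, so every imputed subject is a non-responder. Taking 58.6% (Protocol Table 1.5.3, combined) as illustration and random dropout: 58.6% × 136/161 = 49.5%, about 9 points lower.

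**Successive visits.** Take pain 2.5 at Visit 11, 1.5 at Visit 13, then missing. WOCF gives 2.5 at Visits 15 and 17. The Visit 13–15 difference is +1.0, a worsening nobody observed, and Visit 15–17 is 0. Protocol 10.3.5 and 10.4.2 judge stability by whether the interval includes zero. For a truly stable score at 15% random dropout, the Visit 15–17 interval included zero 90% (pre-treatment counted) or 93% (not counted) of the time under WOCF, against 95% for observed cases. The SEs were 0.052–0.054 against 0.060.

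**The case against.** The strongest defence is that WOCF is a deliberate conservative choice: it moves results against the product, the endpoints are exploratory, and no decision rule depends on them. Observed cases are no safe benchmark either. When dropout follows poor response they err the other way, and WOCF without pre-treatment scores then covers better (89–93% against 80–89%). This last point stands, and it is why observed cases alone should not become primary. The conservatism argument is weaker: there is no test to protect, and the size of the shift hangs on an undefined detail.

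Four stronger readings are tempting, but the documents do not support them:

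- A reader might infer that the protocol forbids carry-forward. Its default has an exception clause, and Protocol 10.5 itself prescribes WOCF. The conflict is over primary versus robustness role.
- A reader might infer that the intervals are too narrow because filled values count as data. Widths in the simulation are about 1.5–8% smaller than for observed cases and by formula can be larger, and the nominal SE is about right for the WOCF mean.
- A reader might infer that every difference after dropout is zero. The first is zero or a worsening; only later ones are zero.
- A reader might infer that all ITT efficacy results are affected. SAP 4.8 names three scores. WOMAC B, time to knee replacement and rescue use lie outside it.

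The 15% is also a loose input: Protocol 10.3.7 words 136 as the number enrolled, SAP 2.4 anticipates 100 subjects and SAP 4.3 about 160. Absolute widths change with the sample size; the shift depends on the missing fraction.

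**Conclusion.** The point holds as an undeclared change of role with a predictable effect on the estimates. Under random dropout of 15%, mean pain change is understated by about 0.13–0.14 points if pre-treatment scores count and 0.02–0.05 if they do not, with coverage of about 41–44% or 88–93%. At 25% random dropout with pre-treatment scores counted, the mean is −0.59 and coverage 5%. The visit-to-visit stability analysis also acquires apparent worsening that was not observed.

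The direction is sure wherever a dropout's worst score is worse than the score that would have been seen. The sizes rest on earlier-study means and SDs and on assumed correlations, baseline distribution and dropout patterns. WOMAC A, WOMAC C, PGA and the responder endpoints derived from them are affected, in the ITT population only. The primary endpoint, treatment-emergent adverse events, is not. Severity is minor to moderate.

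**What to change.** In SAP 4.8:

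- Make the multiple imputation already listed there primary, combined by Rubin's rules, or use a likelihood-based repeated-measures analysis.
- Report observed cases alongside, with the number missing or imputed at each visit.
- Keep WOCF as the robustness analysis of Protocol 10.5.
- State whether pre-treatment scores count for WOCF and, if so, whether this means the main-study baseline, Visit 9 or both.
- Apply one rule to WOMAC A, B and C, the two pain sub-scores and PGA, and say how per-protocol tables treat missing scores.

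Record the choice and the reason in SAP Section 6. This is needed for multiple imputation too, since the default in Protocol 10.3.11.5 is not to estimate missing data.

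The cost is SAP wording and minor extra programming. No data collection changes.

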4.9 Detection of Bias

There is no blinding in this study and thus there is never a situation where any breaking of the blind for individual subjects will be necessary.

4.10 Outliers

No formal outlier tests are planned. Values that are outside the pre-defined range, such as a WOMAC score not between zero and four, or a PGA score not between one and five, would be queried and excluded if necessary prior to database lock.

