6.1.1 WOMAC® Osteoarthritis Index ([Bellamy 1988](#))

WOMAC Index 3.1 should be completed by subjects at each in-clinic visit, pre-dose. All subjects are required to take at least 5 minutes to complete the questionnaire.

Subjects are asked about their pain, stiffness, and function in the study knee (study joint) due to arthritis during the last 24 hours. This will be assessed at every in-office visit.

Subjects will also be asked about their pain, stiffness, and function in the non-study knee. This will be assessed at Enrollment and Visit 17 (or early termination visit).

Subjects respond to each subscale by using a 5-point adjectival Likert score (0 = none, 1 = mild, 2 = moderate, 3 = severe, 4 = extreme).

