6.1.2 Patient's Global Assessment of Disease Severity (PGA)

The PGA should be completed by subjects at each in-clinic visit (prior to injection).

Subjects are asked the following question: “Considering all the ways in which your arthritis affects you, please indicate how you are doing.”

Subjects respond by using a 5-point adjectival Likert score (0 = very well, 1 = well, 2 = fair, 3 = poor, 4 = very poor).

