11.7 COLLECTION, MONITORING AND AUDITING STUDY DOCUMENTATION, AND DATA STORAGE

11.7.1 Collection of Data and Monitoring Procedures

This study will use a 21 CFR Part 11 compliant electronic data capture system (eDC). An electronic case report form (eCRF) is used for data recording. All data requested on the eCRF must be entered and all missing data must be accounted for.

The data will be checked for completeness and correctness as it is entered by the real-time online checks applied by the eDC system. Off-line checks will also be run to perform any additional data review required. Discrepancy reports will be generated accordingly and transferred to the study center for resolution by the investigator or his/her designee.

Accurate and reliable data collection will be assured by verification and cross-check of the eCRF against the investigator's records by the study monitor (source document verification), and the maintenance of a study drug-dispensing log by the investigator.

Before study initiation, at a site initiation visit or at an investigator's meeting, a Sponsor representative will review the protocol and case report forms with the investigators and their staff. During the study a monitor will visit the site regularly to check the completeness of subject records, the accuracy of entries on the case report forms, the adherence to the protocol and to Good Clinical Practice, the progress of enrollment. The monitor will ensure during on-site visits that study medication is being stored, dispensed and accounted for according to specifications. Key trial personnel must be available to assist the monitors during these visits.

The investigator must give the monitor access to relevant hospital or clinical records, to confirm their consistency with the case report form entries. No information in these records about the identity of the subjects will leave the study center. Monitoring standards require full verification for the presence of informed consent, adherence to the inclusion/exclusion criteria, documentation of SAEs and the recording of primary efficacy and safety variables. Additional checks of the consistency of the source data with the eCRFs are performed according to the study-specific monitoring plan.

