3.2 Exploratory Endpoints

The exploratory endpoints in this trial will be assessed at Visit 9 (Enrollment), Visit 11 (Week 12), Visit 13 (Week 24), Visit 15 (Week 36) and Visit 17 (Week 40) and are:

- Responder status based on the OMERACT-OARSI responder criteria
- Evaluate OMERACT-OARSI 'controlled' responder defined as a 20% improvement in Pain and Function and 0.5 point absolute change in the 5-point Likert Scale
- Evaluate 20% improvement in PGA and 0.5 point absolute change in the 5-point Likert Scale
- Mean change and percent change in WOMAC A pain subscore
- Mean change and percent change in WOMAC B stiffness subscore
- Mean change and percent change in WOMAC C physical function subscore
- Mean change and percent change in PGA

- Mean Change and percent change in WOMAC A pain subscore questions 1 and 2 (pain with movement)
- Mean Change and percent change in WOMAC A pain subscore questions 3–5 (resting pain)
- Change in contralateral knee pain (WOMAC A)
- Change in contralateral knee stiffness (WOMAC B)
- Change in contralateral knee function (WOMAC C)
- Time to Total Knee Replacement (TKR)
- Use of rescue analgesia (amount of acetaminophen used)

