For any variable, unless otherwise defined, baseline is the last assessment taken prior to the first study drug administration.

Change from Baseline:

The arithmetic difference between a post-baseline value and the baseline value:

Change from Baseline = (Post-baseline Value – Baseline Value)

Percentage Change from Baseline = [(Post-baseline Value – Baseline Value) / Baseline Value] x 100

End of Study

End of study is at Visit 17 (Day 280 ± 14 days), unless terminated early.

Enrollment date

Enrollment date is the same as the randomization date and is designated Day 0.

Study drug

Study drug in this study is Ampion or saline.

Randomization date

Randomization date is the day the subject is assigned a randomization number on study Day 0.

Study Day 0

Day 0 is defined as the first day that study drug is administered to the subject.

Study Day

Day of treatment: study day = (visit date - date of Study Day 0)

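### The SAP's valid range for PGA (one to five) does not match the protocol's 0-4 scale, so the best score, 0, is flagged and may be excluded

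*SAP*

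**What the plan says.** Protocol 6.1.2 has subjects answer the PGA on a "5-point adjectival Likert score (0 = very well, 1 = well, 2 = fair, 3 = poor, 4 = very poor"). Protocol 6.1.1 codes the WOMAC items in the same way: "5-point adjectival Likert score (0 = none, 1 = mild, 2 = moderate, 3 = severe, 4 = extreme").

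SAP 4.10 plans no formal outlier test but gives two examples of values outside the pre-defined range. The WOMAC example is "such as a WOMAC score not between zero and four", which agrees with the protocol. The PGA example is "or a PGA score not between one and five, would be queried and excluded if necessary prior to database lock", which does not. No section of either document describes a PGA form coded 1-5 or a recoding step. Elsewhere the scale is only called a 5-point Likert scale.

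Three other provisions decide what happens to a flagged score:

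- Protocol 11.7.1, on discrepancies: "Discrepancy reports will be generated accordingly and transferred to the study center for resolution by the investigator or his/her designee".
- SAP 4.8, on missing WOMAC A, WOMAC C and PGA values in the ITT population: worst observation carried forward "will be selected as the primary method of imputing missing data".
- SAP 5.2, on percent change: "Percentage Change from Baseline = [(Post-baseline Value – Baseline Value) / Baseline Value] x 100".

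PGA enters the exploratory analyses as mean change, percent change, a responder endpoint ("Evaluate 20% improvement in PGA and 0.5 point absolute change in the 5-point Likert Scale") and one of the three OMERACT-OARSI domains.

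**The concern.** A range check should remove only values that the instrument cannot produce. This one flags the most favourable answer on the form, so any exclusion under it depends on the outcome. The SAP does not say that a 0 confirmed on query is kept.

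A post-baseline 0 that is excluded and then imputed as the subject's worst observation turns the best possible result into the least favourable one recorded. That would pull mean PGA change and the PGA responder rate against the product. OMERACT-OARSI status could also change, but only for subjects who need the PGA component, because pain and function can qualify a subject without it.

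Zeros at baseline are exposed too, since no entry criterion sets a minimum PGA. Those subjects cannot improve, so losing them would act in the opposite direction.

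If the eCRF in fact codes PGA 1-5, the SAP range is workable and the protocol's scale is the one to correct. The coding would still have to be settled, because percent change divides by the baseline value.

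**Working it through.** **1. Compare the two sets.** Protocol codes: {0, 1, 2, 3, 4}. SAP accepted values: {1, 2, 3, 4, 5}. Valid in the protocol but flagged by the SAP: {0}. Not on the protocol scale but accepted by the SAP: {5}. The protocol's codes therefore do not give the SAP's range.

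**2. Which improvements are exposed.** On 0-4 there are 10 possible improvements (baseline higher than post-baseline). The responder rule is taken as at least 20% and at least 0.5 points, as protocol 10.4.2 writes it for the PGA component. The 1-5 column adds 1 to both scores.

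| Baseline to post (0-4 codes) | % change, coded 0-4 | % change, coded 1-5 | Responder under both |
|---|---|---|---|
| 1 to 0 | -100.0 | -50.0 | yes |
| 2 to 0 | -100.0 | -66.7 | yes |
| 2 to 1 | -50.0 | -33.3 | yes |
| 3 to 0 | -100.0 | -75.0 | yes |
| 3 to 1 | -66.7 | -50.0 | yes |
| 3 to 2 | -33.3 | -25.0 | yes |
| 4 to 0 | -100.0 | -80.0 | yes |
| 4 to 1 | -75.0 | -60.0 | yes |
| 4 to 2 | -50.0 | -40.0 | yes |
| 4 to 3 | -25.0 | -20.0 | yes |

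All 10 are responders under either coding, and 4 of the 10 end in the flagged value 0. Mean change is the same under both codings. Percent change differs in every row. On 0-4, a baseline of 0 gives division by zero.

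**3. Effect on the responder rate, with imputation.** The documents give no PGA distribution, so all inputs here are assumptions: responder rate r = 50%; share of scores equal to 0, p0 = 1%, 5%, 10% or 20%; share of zeros excluded after query, q = 1 (none rescued) or 0.1 (90% rescued). Every zero is taken to be a post-baseline responder and to be imputed as a non-response. Imputation keeps the denominator, so rate = r - q × p0.

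| p0 | q = 1 | q = 0.1 |
|---|---|---|
| 1% | 50 - 1 = 49% | 50 - 0.1 = 49.9% |
| 5% | 50 - 5 = 45% | 50 - 0.5 = 49.5% |
| 10% | 50 - 10 = 40% | 50 - 1 = 49% |
| 20% | 50 - 20 = 30% | 50 - 2 = 48% |

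**4. Effect on mean change.** If w is the value that replaces the 0, the shift is q × p0 × w. With q = 1 and w = 2 (fair), it is 0.02, 0.10, 0.20 or 0.40 points for the four values of p0. This is not an upper bound: with w = 4 the same formula gives 0.04, 0.20, 0.40 or 0.80.

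**5. Without imputation.** If excluded zeros simply drop out, the rate is (r - q × p0) / (1 - q × p0). With q = 1 this is 49/99 = 49.5%, 45/95 = 47.4%, 40/90 = 44.4% or 30/80 = 37.5%.

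**The case against.** The mismatch itself is not in dispute. The case on the other side is that it would do little harm.

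- **The form may govern.** SAP 1 says that data review is to confirm agreement with the CRF categories, and the ranges in SAP 4.10 are introduced as examples. A 0 printed on the form would then conform. But the general wording does not correct the specific number, and a programmer building the edit check would use the number.
- **Exclusion needs several failures.** A 0 must be flagged, go to the site, be confirmed, and still be judged necessary to exclude. Independent programming (SAP 4.11) is another chance to catch the error. This stands: data loss is a risk and not a certainty, and the q = 0.1 column is the more likely kind of result.
- **The route to imputation is not fully settled.** SAP 4.8 does not say that a range-excluded value counts as missing. Protocol 10.3.11.5 does not carry missing data forward in descriptive analyses unless otherwise specified, and protocol 10.5 uses worst observation to assess robustness. SAP 7 also provides per-protocol efficacy tables. This stands in part. SAP 4.8 does name the method as primary for ITT, and step 5 shows that dropping the zeros biases the rate in the same direction, though less.
- **The magnitudes are assumed, and not every imputed 0 becomes a non-response.** A subject with baseline 4 and worst post-baseline score 2 would still respond. This is correct, and it is why the q = 1 rates are a worst case.
- **PGA is exploratory, with no comparator and no formal hypothesis.** Also correct; it limits the importance of the point but not its validity.

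**Conclusion.** The concern holds. SAP 4.10 contains a data-exclusion rule that contradicts the protocol's own PGA scale, and the value it wrongly flags is the best score. That conclusion needs no assumption beyond the text of the two documents.

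The size of any effect cannot be derived from them. It depends on how many scores are 0 and how many survive the query process, and it could be negligible or, in the worst case shown, as large as 20 percentage points on the PGA responder rate. The consequence is confined to exploratory endpoints: PGA change, PGA percent change, the PGA responder rate and, for some subjects, OMERACT-OARSI status. The primary endpoint, incidence and severity of treatment-emergent adverse events, is untouched.

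The correction should be made, but it does not threaten the study's main purpose. If the eCRF turns out to code 1-5, mean change and responder status are unaffected, and what remains is an undefined basis for PGA percent change (fair to well is -50% or -33%).

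**What to change.** 1. Check how PGA is coded on the eCRF.
2. If it is 0-4, change the PGA range in SAP 4.10 to zero to four. If it is 1-5, correct protocol 6.1.2 or state an explicit recode, so that both documents use one coding for percent change.
3. Add to SAP 4.10 that a value valid on the form is never excluded, and that only impossible values still unresolved after query are set to missing.
4. As a side point, if the coding is 0-4, state how percent change is handled when the baseline is 0.

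The cost is one look at the eCRF, a short SAP edit (or one protocol clarification) and one edit-check specification. It should be done before database lock, because SAP 4.10 places the exclusions before lock.
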